12.0 Data and Specimen Banking

There is no a priori data sharing plan for data or specimens. Blood specimens were centrally analyzed by both the Northwest Lipid Research Laboratory (University of Washington, Seattle) until they closed in July of 2020, and then by Advanced Research Diagnostics Laboratory (ARDL) (University of Minnesota, Minneapolis). No stored samples were banked. An investigator with interest in the data files for this study would need to contact the PI at [contact].

13.0 Sharing of Results with Subjects

The data collected in this study are specific to the research and are not designed to assess medical conditions. The investigators are not responsible for failure to find existing abnormalities. In the unlikely event that a participant's data (e.g., bloodwork biometrics) show a possible abnormality, the PI or Co-I (Study MD) contacts the participant and advises medical follow-up for the problem, including a referral

Reducing cardiometabolic risk and promoting functional health in community-based elders with obesity and pre-diabetes: evaluating sustainable follow-up strategies

to a primary care provider (PCP). For participants who already have a PCP, and provide verbal permission, the study doctor may inform the PCP of the finding and determine if follow-up is advisable. The decision as to whether to proceed with further examination and/or treatment lies solely with a participant and their PCP. The study does not cover the costs of any follow-up actions.

End of study information provided: Participants will be mailed a letter from the PI describing the results of the study, including a copy of the main outcomes paper when available.

14.0 Withdrawal of Subjects

Participants may be withdrawn from the research without their consent under the following circumstances:

- the investigator decides that continuation can be harmful to the participant,
- participant develops a new condition or undergoes treatment that will make their subsequent follow-up data in the study unusable,
- the study is cancelled, or there are other administrative reasons.

In the event a participant withdraws or is asked to leave the study, they will still be compensated for the study activities they have completed.

15.0 Risks to Subjects

This is a minimal risk study with prudent measures in place to protect the health and well-being of research participants and their privacy and confidentiality. Risks associated with participation in this study include the following:

- (1) Potential risks associated with reduced caloric intake and increased physical activity, such as musculoskeletal injuries.
- (2) Patient privacy and confidentiality breach.
- (3) Inconvenience associated with data collection.

These risks are mostly associated with the characteristics of the target patient population and the procedures involved in the research. The risks are reasonable in relation to the anticipated benefits and will be minimized by using sound clinical research procedures and risk mitigation strategies. Although we cannot guarantee that risks will not occur, we will implement the following measures to minimize potential risks to participants in the study.

Protection against Risks Associated with Weight Loss Strategies. The premise of the study is that prudent yet comprehensive lifestyle interventions, which include evidence-based strategies for dietary modification, physical activity and behavior change, are necessary to meet the targets set forth in national guidelines for managing obesity and obesity-related cardiometabolic and other comorbidities. By managing BMI according to these evidence-based guidelines for intensive behavior therapy, intervention participants may be exposed to risks associated with caloric reduction and physical activity not experienced in routine care.

The interventions to be tested in this clinical trial promote a balanced, calorie-controlled diet approach and recommend against very low-calorie diets (<1200 kcal/day) or losing weight too rapidly (> 2 lbs.

Reducing cardiometabolic risk and promoting functional health in community-based elders with obesity and pre-diabetes: evaluating sustainable follow-up strategies

per week). Participants will be advised to avoid crash or fad diets that promise marked, rapid weight loss. Instead, they will be advised to adopt a moderate caloric reduction by 500-1000 kcal/day through healthy substitutions and portion control, rather than omission or elimination of specific foods or food groups. Given the average age anticipated in this participant sample, the intervention will encourage consumption of plant-based and lean-meat proteins and low-fat or fat-free dairies at most meals. The selection of low-calorie, nutrient-dense foods in accordance with USDA-recommended healthy dietary patterns will be emphasized. Participants who wish to lose additional weight after reaching the program's weight loss goal (5-10% of baseline weight) will be encouraged to do so only insofar as they maintain a normal BMI and the rate of weight loss does not exceed 2 lb/week.

To minimize risks associated with increased physical activity, consistent with the current public health physical activity recommendations for Americans, the study interventions promote achieving 150 minutes or more per week of moderate-intensity physical activity in a gradual manner. If participants reach the 150-minute goal but are not achieving the weight loss goal, they can gradually increase to 60-90 minutes/day of moderate physical activity, as tolerated. We will also recommend resistance training activities 2 times per week, consistent with NIA public health guidelines. Moderate-intensity physical activity is deemed feasible for adults with chronic conditions or functional limitations, and the benefits are believed to outweigh the risks. We will emphasize brisk walking—a physical activity recommended as being safe for most adults—as the preferred mode of exercise. Participants will receive information about how to be active safely considering their conditioning, interest, context, and environment.

Protection against Breaches of Participant Privacy and Confidentiality. All information to be obtained during the study will be considered strictly confidential and only used and disclosed as permitted under the HIPAA regulations. All eligible patients must sign the HIPAA authorization as a part of the informed consent to participate. Only aggregate data will be included in scientific presentations and publications resulting from this study; the identity of individual participants will not be revealed. In addition, the following measures will be taken during the conduct of the study to ensure adequate protection of participant privacy and confidentiality:

- All investigators and staff will be adequately trained to protect participant privacy and sign an agreement to do so.
- Personal identifiable information (PII) and protected health information (PHI) collected for the purpose of the research study will be assigned a unique anonymous study ID number. The study IDs will be used on all study forms and for data storage, tracking and reporting.
- Both the anonymized health information and the information linking the study ID numbers to participants' identities will be stored in a password protected database on a secure network fitted for protection of such information, which will be accessible only to the research personnel who have a need to know.
- The information linking the study ID numbers to participants' identities will be stored separately from the anonymized health information.
- We will follow the latest industry standards for data encryption, server authentication, and client authentication to ensure secure data transmissions at all times.
- No participant data, even if de-identified, shall be saved onto any portable devices, such as laptop computers or USB drives.

Protection against Risks Associated with Data Collection. All study measures are either objectively measured by trained research staff, or self-measured or self-reported by participants. There are no greater risks associated with completing the required measurements in this study than those ordinarily

Reducing cardiometabolic risk and promoting functional health in community-based elders with obesity and pre-diabetes: evaluating sustainable follow-up strategies

associated with such measurements in routine health care. For surveys and questionnaires, participants are reminded at each assessment that they do not have to answer any question they do not wish to answer.

16.0 Potential Benefits to Subjects

Although several potential benefits may be expected from participating in this study, we cannot guarantee that any individual participant will experience these benefits. All participants, including the Placebo Comparator, will receive an evidence-based lifestyle intervention aligned with the MDPP. The interventions to be tested promote modest weight loss through healthy eating, increased physical activity, and behavioral self-management. These healthy lifestyle factors have known health benefits, including but not limited to, lowering the risk of type 2 diabetes for those at high risk as well as prevention and control of hypertension and hyperlipidemia. Improvements in these lifestyle factors and health outcomes may in turn lead to better quality of life. All the benefits are likely to be long-term and outweigh any possible short-term risks.

17.0 Data Management and Confidentiality

Data Management.

Data security.

18.0 Data Analysis Plan

All analyses are conducted in consultation with the study biostatisticians, using SAS 9.4 (SAS Institute, Inc., Cary NC). Descriptive analyses and graphic displays are used to identify outliers, missing data, and patterns of attrition. Demographic variables and baseline measures are contrasted between the Active Comparator: DPP-Behaviorally Intensive 30-Minute Groups (DPP-BI) and the Placebo Comparator: DPP Minimal 15-minute Calls (DPP-MIN) conditions. In all outcome analyses we will use an intent-to-treat (ITT) approach in which participants remain in the study arm to which they are randomized regardless of attrition. The primary analytic strategy is a linear or generalized mixed-effect models approach in which treatment group, time, and time by group interaction are treated as fixed effects, and subject is treated as a random effect to account for individual subject variability. Hypothesis tests are two-sided, and significance will be set at the 0.05 level. Mixed models are applicable to longitudinal datasets that contain missing observations, with the assumption that the data are missing at random. Our prior intervention studies suggest that we can anticipate 90% retention at 6 months and greater than 80% retention over the 18-month extended intervention period (at 24 months) with no differential attrition between arms. Those who drop out or are lost to follow-up are compared to those who have completed intervention for research assessments using standard parametric and non-parametric methods, as appropriate. We will examine the patterns of missingness and, if necessary, account for missingness in outcome analysis (e.g., the covariate approach). Regression modeling will be conducted to adjust for covariates such as race, sex, age, socio-demographic factors, and other designated baseline clinical variables.

Research Questions

Reducing cardiometabolic risk and promoting functional health in community-based elders with obesity and pre-diabetes: evaluating sustainable follow-up strategies

Analysis Plan for Hypotheses 1 and 2: We will apply mixed effect models to evaluate differential changes in weight measures at 6, 12, 18, and 24 months from baseline, with fixed terms of group (DPP-BI vs. DPP-Min), time as a factor (6,12,18, and 24 months), and the group by time interaction. We employed the following steps as the pre-randomization balancing logic: (1) group subjects by weight loss status (≤ 3.5 vs. > 3.5 percent at 6-months) and age (≤ 70 vs. > 70 years at baseline), (2) group subjects by sex (male vs. female) and race (Black/African American or Black/Mixed/Other vs. White/Caucasian), (3) group subjects using all 4 factors (based on 2x2 frequency table) and (4) randomly assign the subjects in the same cell into 2 conditions (DPP Plus vs. DPP Minimal). Subject was included as a random term. To test the differential treatment effect, evaluated the coefficients that are associated with the group and the group by time interaction by using an F test. Planned contrasts will be set up from the mixed models to compare the improvement in weight from baseline to Months 12, 18 and 24 between the two conditions (DPP-BI vs. DPP-Min). In addition, a generalized mixed-effect model was fit to the binary outcome of achieving $\geq 5\%$ weight loss at 6, 12, 18, and 24 months, with the logit link, which includes similar fixed and random terms as above. Average percent weight loss and the proportions achieving $\geq 5\%$ weight loss are compared between the two groups at 12, 18 and 24 months. Similar analyses were performed for fasting glucose, HbA1c, and insulin (and other biometric measures), physical activity/function, and other secondary outcomes at subsequent assessment points.

The planned contrasts were set up to compare differential changes from baseline to Months 12, 18, and 24. Benjamini-Hochberg's method was used to control for the overall type I error for multiple secondary outcomes. More intensive modeling is performed to account for factors that are known to affect the outcomes as well as those that have been found to differ between treatment conditions at baseline and at Month 6 (the timepoint at which participants are stratified by $<$ or $\geq 3.5\%$ weight loss and other factors and randomly assigned to the two 18-month conditions). We also perform analyses in which we restrict our linear and generalized mixed-effect analyses to those who did not reach $\geq 5\%$ weight loss at 6 months and set up the contrasts to compare DPP-BI with DPP-MIN, on average, and the proportion reaching $\geq 5\%$ at 12 months and 18 months from baseline.

Exploratory Aim. We examine available Medicare data for those insured by a large regional payer to assess group and time from baseline differences in medical utilization metrics (e.g., type of outpatient, inpatient, or emergency visits) and participation in activity programs, for a proportion of the sample. We will extract Medicare data on numbers of outpatient, inpatient and emergency visits, and number of subjects participating in activity programs, and compare the numbers between the two conditions using linear and generalized regression models. We will explore the potential moderation effects of sex and race. We will include the interaction of sex by group or race by group in the mixed-effect models, as well as the three-way interaction of sex, group and time or race, group and time, if the group by time interaction is significant in the original model.

Reducing cardiometabolic risk and promoting functional health in community-based elders with obesity and pre-diabetes: evaluating sustainable follow-up strategies

Power and Sample Size Considerations. We powered this study on the main comparisons between the Active Comparator: DPP-BI and the Placebo Comparator: DPP-MIN on average weight loss at 12 months from baseline (24-month data is not readily available). With 180 subjects per arm and projected 90% attrition at Month 12, we would have 80% power to detect effect sizes of 0.31, using two-sided t tests at the 0.05 level. Our prior Pitt Retiree study observed approximately 7.5 % weight reduction at 12 months among those subjects who received active intervention for 12 months, and 5.5% reduction at 12 months among those in the placebo comparator group. Assuming similar effects and similar standard deviation of 5.8% as observed in the Pitt Retiree study, we expect to see a standardized group difference ranging 0.34 at Months 12 between DPP-BI and DPP-MIN. Hence we anticipate that our projected sample size will enable us to detect group differences with power greater than 0.8 for our primary weight outcome.

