4.0 Study Endpoints

The Sustain study primary endpoint is 24-months, and important secondary endpoints are examined at 18, 12, and 6-months. All study endpoints are indexed from baseline assessment; however, randomization does not occur until the six-month assessment.

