Analysis Plan for Hypotheses 1 and 2: We will apply mixed effect models to evaluate differential changes in weight measures at 6, 12, 18, and 24 months from baseline, with fixed terms of group (DPP Plus vs. DPP Minimal), time as a factor (6,12,18, and 24 months), and the group by time interaction. We will employ the following steps as the pre-randomization balancing logic: (1) group subjects by weight loss status (≤ 3.5 vs. > 3.5 percent at 6-months) and age (≤ 70 vs. > 70 years at baseline), (2) group subjects by sex (male vs. female) and race (Black/African American or Black/Mixed/Other vs. White/Caucasian), (3) group subjects using all 4 factors (based on 2x2 frequency table) and (4) randomly assign the subjects in the same cell into 2 conditions (DPP Plus vs. DPP Minimal). Subject will be included as a random term. To test the differential treatment effect, we will evaluate the coefficients that are associated with the group and the group by time interaction by using an F test. Planned contrasts will be set up from the mixed models to compare the improvement in weight from baseline to Months 12, 18 and 24 between the two conditions (DPP Plus vs. DPP Minimal). A generalized mixed-effect model will be fit to the binary outcome of achieving $\geq 5\%$ weight loss at 6, 12, 18, and 24 months, with the logit link, which includes similar fixed and random terms as above. Average percent weight loss and the proportions achieving $\geq 5\%$ weight loss will be compared between the two groups at 12, 18 and 24 months. We will perform similar analyses for fasting glucose, HbA1c, and insulin (and other biometric measures), physical activity/function, and secondary outcomes at subsequent assessment points.

The planned contrasts will be set up to compare differential changes from baseline to Months 12, 18, and 24. Benjamini-Hochberg's method will be used to control for the overall type I error for multiple secondary outcomes. More intensive modeling will be performed accounting for factors that are known to affect the outcomes as well as those that have been found to differ between treatment conditions at baseline and at Month 6 (the timepoint at which participants are stratified by $<$ or $\geq 3.5\%$ weight loss and other factors and randomly assigned to the two 18-month conditions). We will also perform analyses in which we restrict our linear and generalized

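### The main model for the continuous Hypothesis 2 outcomes compares change from Month 0 without pre-specifying the outcome's own Month-0 value as a term, so its contrasts are less precise than the collected data allow

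*Protocol*

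**What the plan says.** Under the analysis plan for Hypotheses 1 and 2 (protocol section 18.0), the mixed models are to "evaluate differential changes in weight measures at 6, 12, 18, and 24 months from baseline". The fixed terms are group, "time as a factor (6,12,18, and 24 months), and the group by time interaction", with subject as a random term. Month 0 is not a level of time.

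The same approach is carried to Hypothesis 2: "Similar analyses were performed for fasting glucose, HbA1c, and insulin (and other biometric measures), physical activity/function, and other secondary outcomes". The SAP matches: "We will perform similar analyses for fasting glucose, HbA1c, and insulin (and other biometric measures), physical activity/function, and secondary outcomes". On the contrasts the protocol adds: "The planned contrasts were set up to compare differential changes from baseline to Months 12, 18, and 24".

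Both documents present the model with group, time and interaction as the main analytic approach. Two other sentences bear on adjustment. One promises regression to "adjust for covariates such as race, sex, age, socio-demographic factors, and other designated baseline clinical variables". The other reads "More intensive modeling is performed to account for factors that are known to affect the outcomes", and extends to factors found to differ between arms at baseline or Month 6. Neither names the outcome's own baseline value, lists the designated variables, or says whether the adjusted or unadjusted result decides Hypothesis 2.

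On timing, protocol section 4.0 states: "All study endpoints are indexed from baseline assessment; however, randomization does not occur until the six-month assessment".

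**The concern.** A contrast from baseline is possible in a model without a Month-0 level only if the response is already a change score. With complete data, each planned contrast is then the plain difference between arms in mean change. The error in the single Month-0 reading enters every 12-, 18- and 24-month comparison in full. A chance difference between arms at Month 0 also feeds into the change scores through regression to the mean.

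This matters more for measures with modest visit-to-visit correlation than for weight. Hypothesis 2 covers many outcomes, faces a Benjamini-Hochberg correction, and has no stated power for any of them. Precision given away here is not made up elsewhere in the plan.

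**Working it through.** **The plan's own figure.** The only power statement concerns weight at Month 12: 180 per arm, effect size 0.31, two-sided 0.05, 80% power. It reproduces if the stated 90% attrition is read as 90% retention: 180 × 0.9 = 162 per arm gives 79.7% power and a detectable effect of 0.311. Read literally (18 per arm), power would be 15%. No comparable figure exists for a Hypothesis 2 outcome, so what follows is relative precision, which does not depend on sample size.

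**Inputs.** The model terms and response come from section 18.0 and the SAP. The Month-0 to follow-up correlation ρ and the SD ratio k = SD(Month 0)/SD(follow-up) are in neither document. I assume ρ from 0.4 to 0.8 and vary k.

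**Formulas**, in units of the follow-up variance:
- change score: 1 + k² − 2ρk
- adjusted for Month 0: 1 − ρ²
- difference between the two: (k − ρ)², which is never negative, so in large samples adjustment cannot lose precision.

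With k = 1 the ratio of adjusted to change-score variance is (1 − ρ²)/[2(1 − ρ)] = (1 + ρ)/2. The variance reduction is (1 − ρ)/2, and the unadjusted SE is wider by a factor √[2/(1 + ρ)].

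**Adjusting for Months 0 and 6.** If Month 0, Month 6 and follow-up have equal SDs and equal pairwise correlation ρ, the adjusted variance is 1 − 2ρ²/(1 + ρ). At ρ = 0.4 this is 1 − 0.32/1.4 = 0.771, against 1.2 for change: a 36% reduction. At ρ = 0.8 it is 1 − 1.28/1.8 = 0.289, against 0.4: a 28% reduction.

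| ρ | Variance reduction, Month 0 only | Unadjusted SE wider by | Variance reduction, Months 0 and 6 |
|---|---|---|---|
| 0.4 | 30% | 19.5% | 36% |
| 0.6 | 20% | 11.8% | 31% |
| 0.8 | 10% | 5.4% | 28% |

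In power terms at 144 per arm (80% of 180), an effect with 80% power unadjusted has 92%, 88% or 84% power with the Month-0 value and 94%, 92% or 91% with both values, at ρ = 0.4, 0.6 and 0.8.

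**Unequal SDs, Month 0 only.** With k = 0.8:
- ρ = 0.4: 1 − 0.84/1.00 = 16%
- ρ = 0.6: 1 − 0.64/0.68 = 6%
- ρ = 0.8: 1 − 0.36/0.36 = 0%

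With k = 0.7 the reductions are 10%, 1.5% and 3%. With k = 1.1 they are 37%, 28% and 20%.

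**Checks.** Simulation at ρ = 0.5 and 0.7 with equal SDs gave variance ratios of 0.76 and 0.85 (theory 0.75 and 0.85). A random-intercept model fitted to one complete simulated data set of change scores, with group by time, returned a Month-24 contrast identical to the raw difference in mean change (0.157). The random subject term therefore does not recover the lost precision.

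**The case against.** The best defence is that the plan does not rule out adjustment. The covariate sentence belongs to the general strategy and is not labelled secondary. The further modelling covers prognostic factors and those found unbalanced, and an outcome's own baseline fits both descriptions. So a reader who infers that the plan never adjusts for baseline goes too far. What remains is that the value is not named, the designated variables are not listed, part of the adjustment depends on imbalance seen in the data, and the deciding model is not identified.

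The size is also open to challenge. A reader might take a 10% to 30% loss as established. It is a variance figure that rests on assumed correlations and equal SDs. Section 7.0 restricts glucose or HbA1c at entry, which could narrow the Month-0 spread and bring the gain for those two close to zero. This is not certain even for HbA1c, because section 10.0 describes a separate finger-stick screen before the baseline visit. The entry limits do not directly restrict the other outcomes.

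Two further inferences lack support. One is that insulin and triglycerides are to be analysed untransformed: the documents state no scale. The other is that every Hypothesis 2 outcome goes through the change-score model: the plan allows generalized models, which could serve for counts such as falls. The point is therefore limited to continuous outcomes.

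Finally, randomization protects the unadjusted contrast from bias, its type I error is not at issue, and no power claim is contradicted because none is made for these outcomes. All of that stands.

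**Conclusion.** The point holds as one of efficiency and incomplete specification, not validity. The main model for the continuous Hypothesis 2 outcomes omits the outcome's own Month-0 value, and the promised adjusted analyses do not clearly supply it.

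The cost lies between nothing and about 30% of the contrast variance over the assumed ρ of 0.4 to 0.8, for a Month-0 SD no larger than the follow-up SD. The upper part of that range needs low correlation and similar SDs. Because the large-sample variance with adjustment is never worse, uncertainty about the size is no reason to leave the term out.

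Adjusting for Month 0 alone would be incomplete. Randomization is at Month 6, so the Month-6 value also precedes assignment, yet the model treats it as an outcome visit. At ρ = 0.8, Month 0 alone recovers 10% of the variance against 28% with both values, if the correlations are equal.

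**What to change.** For each continuous Hypothesis 2 outcome, state in the SAP and in protocol section 18.0 that:
- the primary model takes Months 12, 18 and 24 as the outcome visits;
- it includes the outcome's Month-0 value and its Month-6 (pre-randomization) value as covariates, each with its interaction with visit;
- the arm contrasts at those three visits come from this model and decide Hypothesis 2, and any other adjusted model is supportive.

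The cost is a few sentences and the added covariate terms. Both readings are already scheduled for every participant. The one downside is that a simple rule is needed for a missing Month-0 or Month-6 value; a participant without a Month-0 value has no change score under the present plan either. Parts of section 18.0 are written in the past tense. If the unadjusted contrasts have already been run, the change should be dated and both results reported.

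As a separate and optional matter, the SAP could state the analysis scale for insulin and triglycerides, for example the log scale with effects reported as ratios.
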